9.8.2 ADVERSE EVENTS

AEs that started on or after the first trial treatment will be categorized as TEAEs; whereas AEs that started on or after signing ICF but prior to first trial treatment will be categorized as pre-treatment AEs.

TEAEs reported as definitely, probably, or possibly related to the trial treatment will be deemed as trial treatment-related TEAEs for the purpose of reporting.

On-treatment AEs will be defined as any AE recorded in the trial database, started on or after the first trial treatment until 4 weeks from the last trial treatment (i.e., date of last trial treatment +28 days inclusive).

AESI will be programmatically derived based on [Appendix 3: Sponsor-Defined List of Preferred Terms](#). As ongoing pharmacovigilance could reveal new relevant Standardize MedDRA Queries (SMQs) or Customer Queries (CQs), the final selection will be determined at the data review meeting prior to database lock. The additional changes to this plan can be found in [Appendix 4: Addendum to Statistical Analysis Plan](#).

All AEs will be coded using MedDRA version 24.0 or higher.

An overall summary of AEs will be presented, which will include the incidence (%) of subjects with at least one pre-treatment AE, TEAE, treatment-emergent serious adverse event (TESAE), treatment-emergent AESI (programmatically derived as described above), trial treatment-related TEAE, trial treatment-related TESAE, TEAE leading to trial treatment dose increased, dose reduction of trial treatment, dose interruption of trial treatment, permanent discontinuation of trial treatment, not entering 4 weeks of safety follow-up, follow-up discontinuation, AE leading to death, and on-treatment AE along with the number of events.

The incidence (%) of subjects experiencing AEs for the following categories will be further summarized by SOC and PT in separate tables:

- TEAE

- Treatment-emergent AESI (programmatically derived)
- Trial treatment-related TEAE
- TEAE by severity
- On-treatment AE
- TESAE
- Non-serious TEAE
- Trial treatment-related TESAE

Subjects may report more than one event per coded term. For incidence (%) of subjects, subjects will be counted only once per given SOC or per given PT within SOC. This will also apply to the analysis of TEAEs by severity based on the highest severity. Note: For the summary of treatment-emergent AESI, AESI categories will be used for analysis instead of SOC. The additional changes to this plan can be found in [Appendix 4: Addendum to Statistical Analysis Plan](#).

All AEs will be listed. There will be separate listings for AESIs, SAEs and for AEs leading to permanent discontinuation of trial treatment. All AE listings will include a flag to indicate pre-treatment AE vs. TEAE.

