5.1.10.6 Adverse Events

All AEs will be recorded using the AE pages of the eCRF. AEs will be reported using a recognized medical term or diagnosis that accurately reflects the event. AEs will be assessed by the Investigator for severity, relationship to the investigational product or a protocol requirement, possible etiologies, and whether the event meets criteria as a SAE and thus requires immediate notification of the Sponsor. Definition of SAEs is presented in Section 6.2 and guidelines for assessment of severity and relationship are presented in Section 6.2.6 and Section 6.2.3, respectively. If the event has not recovered to baseline or Grade 1 at the end of the trial reporting period, it will be documented as ongoing for all events that are at least possibly related to trial treatment. If an AE evolves into a condition which becomes “serious” it will be reported as an SAE.

Any laboratory abnormality will be considered an AE if it is judged to be medically significant by the Investigator.

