5.2.3 Visit 3 (Day 0)

- Body weight
- Vital signs (systolic and diastolic blood pressure, heart rate, and axillary temperature)
- Data will be recorded for:
 - Changes in concomitant medications
 - Prescribed PS volume, and composition and days of week
- Any new AE will be recorded, and existing AEs will be followed up
- Gastrointestinal health history: vomiting, nausea, and/or abdominal pain in the preceding 7 days will be recorded
- Administer IMP
- Instruct subject on IMP handling and administration at home
- Dispense IMP

This visit may be delayed for up to 2 weeks, if needed, for scheduling purposes. However, the day of the week of this visit must allow the correct administration of trial medication during the following metabolic study on Day 2.

Subjects to be contacted by telephone on Day 1 (+1 day) to assess fluid overload and stool frequency, any AEs will be collected and any change in concomitant medications will be recorded.

5.2.4 Visit 4

- Data will be recorded for:
 - Changes in concomitant medications
 - Prescribed PS volume, and composition and days of week
- Body weight
- Vital signs (systolic and diastolic blood pressure, heart rate, and axillary temperature)
- Any new AE will be recorded, and existing AEs will be followed up
- Investigator narrative
- Change in eating/appetite
- Blood samples will be collected for:
 - Clinical chemistry including liver enzymes and assessment of creatinine clearance
 - Hematology
 - Hemostasis
 - Serum pregnancy test for premenopausal women
 - Citrulline
 - Pharmacokinetics
 - Anti-drug antibodies

- Urine sample will be taken at the visit for urinalysis and one sample collected during 48-hour urine balance period for sodium analysis.
- The subject e-diary will be reviewed
 - Administered PS volume, days of week
 - Duration of PS infusion
 - Drinking diary: frequency and volume
 - Bristol Stool Form Scale (see Section 5.1.4.1)
 - Frequency of bowel movement
 - Urinary output: frequency and volume
 - Body weight
- IMP administered and dispensed (home used IMP vials to be returned)

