7.6 Safety Analysis

7.6.1 Adverse Events

All AEs occurring from ICF signature and prior to first dose of IMP will be recorded as pre-treatment AEs. All AEs occurring after first dose of IMP and up to the 4 weeks follow-up visit are to be reported as treatment-emergent adverse events (TEAEs). Adverse event summaries will be produced for TEAEs by treatment group including number of subjects with an event, percentage of subjects with an event, and total number of events. In addition, similar separate tables will be produced for each category of severity.

Similar summaries will be made for SAEs, SMQs, and CQs. The relevant SMQs and CQs will be defined in the SAP.

The verbatim terms used in the eCRF by Investigators to identify AEs will be coded using MedDRA (version 23.1 or above).

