7. ENDPOINTS

7.1 PRIMARY ENDPOINT

The following primary endpoints are applicable to the protocol version 4:

- Adverse events (system organ class, frequency, and severity)
- Adverse events of special interest (AESIs)
 - Injection site reaction
 - Gastrointestinal obstruction
 - Gallbladder, biliary and pancreatic disease
 - Fluid overload
 - Colorectal polyps
 - Malignancies
- Clinical chemistry, hematology, hemostasis, ADA, and urine analysis

The following primary endpoint is applicable to the protocol version 3:

- Absolute change in absorption of energy over MB periods from baseline to Week 48

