10. DEVIATIONS FROM ANALYSIS DESCRIBED IN THE PROTOCOL

The following update has been made from the planned analysis defined in the protocol to align the safety analysis plan as defined in the TA799-007 study.

- In the protocol, TEAE is defined as all AEs occurring after first dose of trial medication and up to the 4 weeks follow-up visit. However, for the safety analysis, TEAE will be defined as any adverse events that started on or after the first dose of trial medication (i.e. no longer depends on 4 weeks follow-up visit).

There is one deviation from the planned analysis described in the protocol. According to the protocol, the primary endpoint AESIs are to be derived based on SMQ or CQs. Sponsor issued NTF (See [Appendix 4: Addendum to Statistical Analysis Plan](#)), to clarify that AESI will be identified by using the investigator's assessment, reported in eCRF for analysis.

In addition, the following list contains typographical error (typo) corrections from the protocol that have been made to this SAP for clarity:

- The protocol refers to 'change in absolute absorption'. It is clarified in SAP that this refers to 'absolute change from baseline' in comparison to 'relative change in absorption'. Note: This SAP uses 'absolute change from baseline' and 'change from baseline' interchangeably.
- One of the secondary efficacy endpoints defined in the protocol is 'clinical responder at Week 52' but unlike the protocol synopsis and Section 1.5.2.2 of the protocol, Section 7.1.2 of the protocol indicated Week 48 instead of Week 52. This typo has been corrected to Week 52 in this SAP.
- One of the efficacy endpoints defined in the protocol is 'change in dietary intake of wet weight, energy, macronutrients, fluid, electrolytes (sodium, potassium, calcium, and magnesium) from baseline at Week 4 and Week 48', but this 'fluid' is a part of weight as oral fluid; hence, this text, 'fluid', is omitted in this SAP.
- One of the efficacy endpoints defined in the protocol is "change in fecal excretion of wet weight, energy, macronutrients, fluid and electrolytes (sodium, potassium, calcium, and magnesium) from baseline at Week 4 and Week 48", but this "fluid" is a part of wet weight (urine), which has already been covered by urine output as a part of the secondary efficacy endpoint; hence, the text, 'fluid', is omitted in this SAP.

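### The TEAE rule looks only at the AE start date, so a pre-dose AE that worsens or turns serious on apraglutide drops out of the treatment-emergent tables if it is kept as one record

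*SAP*

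**What the plan says.** SAP 9.8.2 sorts adverse events by start date. For treatment-emergent events it says "AEs that started on or after the first trial treatment will be categorized as TEAEs", and for the earlier period "AEs that started on or after signing ICF but prior to first trial treatment will be categorized as pre-treatment AEs". On-treatment AEs also need a start on or after first dose, and no later than 28 days after the last.

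SAP 10 reopens the definition to align it with TA799-007: "TEAE will be defined as any adverse events that started on or after the first dose of trial medication". The change it discloses is at the end of the window, where the limit at the 4-week follow-up visit is removed. It does not mention worsening. Protocol 7.6.1 speaks of AEs occurring after first dose and also has no worsening clause.

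On recording, Protocol 5.1.10.6 says "If an AE evolves into a condition which becomes" serious, it is to be reported as an SAE. The instruction at Visit 3 (Protocol 5.2.3) is "Any new AE will be recorded, and existing AEs will be followed up". Neither text says whether worsening opens a new AE record, or which date then sets the TEAE flag.

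Under protocol version 4, AEs summarised by system organ class, frequency and severity are part of the primary endpoint (SAP 7.1), alongside AESIs and "Clinical chemistry, hematology, hemostasis, ADA, and urine analysis".

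**The concern.** Safety and tolerability is the primary objective, and the trial has no control arm. The AE part of the primary endpoint reaches the reader mainly through the system organ class and preferred term tables in SAP 9.8.2, and all of these require a start on or after first dose. An event that was mild in screening and becomes severe or serious on drug is one that such a trial should count. If its record keeps the screening start date, the tables do not show it.

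The rule also runs against the plan's own logic elsewhere. Protocol 6.2 keeps conditions present at the initial visit out of the AE data only when they do not worsen. Protocol 5.1.10.5 requires worsening ECG findings to be recorded as AEs. SAP 9.3 settles missing relationship, intensity and seriousness by the worst case. The start-date rule errs in the opposite direction.

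**Working it through.** The documents give no figure on this point, so there is none to reproduce. The check is a reading of the rule against each output, followed by a sense of scale.

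**Step 1. Follow one event.** Take an AE that starts after consent, is ongoing at first dose at Grade 1, and reaches Grade 3 or becomes serious on treatment. Assume it is one record with its pre-dose start date.

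| Output (SAP section) | Condition | Is the event there? |
|---|---|---|
| TEAE by SOC and PT (9.8.2) | start on or after first dose | No |
| TEAE by severity (9.8.2) | TEAE | No |
| Related TEAE, TESAE, related TESAE, non-serious TEAE (9.8.2) | TEAE | No |
| Treatment-emergent AESI (9.8.2) | treatment-emergent | No |
| On-treatment AE (9.8.2) | start on or after first dose | No |
| Pre-treatment AE row of overall summary (9.8.2) | start from consent to before first dose | Yes |
| Row for AEs leading to death (9.8.2) | not worded as TEAE | Yes, if fatal |
| Listings of AEs, AESIs, SAEs and permanent discontinuations (9.8.2) | those AEs, flagged pre-treatment or TEAE | Yes, where they apply |
| CTCAE laboratory shift tables (9.8.3) | baseline to worst post-baseline grade | Yes, for a graded laboratory value |

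**Step 2. Is there room for such events?** Informed consent is taken at Visit 1. By Protocol 5.2.1, Visit 1 is 14 to 28 days before Visit 2, and Visit 2 starts at Day -7 (Protocol 5.2.2). Visit 3, with the first dose, may be delayed by up to 14 days (Protocol 5.2.3).

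- By that text: 14 + 7 = 21 days to 28 + 7 = 35 days; with the full delay, 35 + 14 = 49 days.
- By the day labels in Table 1 (Day -28 to -14): 14 to 28 days; with the full delay, 28 + 14 = 42 days.

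The window contains an endoscopy or colonography and a 5-day admission. Subjects are phoned every 7 days about AEs, vomiting, nausea and abdominal pain (Protocol 5.2.1). These overlap with earlier apraglutide findings: nausea in 75% of patients in GLY-321-2017, and abdominal pain as the one SAE in that trial judged related (Protocol 1.7.2). The events are plausible, but their number is not known.

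**Step 3. Scale.** SAP Section 2 gives 2 + 7 = 9 enrolled subjects. Assume all 9 were dosed. One subject in a row is 1/9 = 11.1 percentage points. Exact (Clopper-Pearson) 95% intervals are:

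- 0/9 = 0.0%: 0 to 33.6%, where the upper limit is 1 − 0.025^(1/9) = 0.336
- 1/9 = 11.1%: 0.3 to 48.2%
- 2/9 = 22.2%: 2.8 to 60.0%

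Subjects count once per SOC or PT (SAP 9.8.2), so a row moves only if the subject has no other TEAE in it. In the severity table it also moves if the added event is that subject's worst. These figures show what one event would do. They do not estimate how many were missed.

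**The case against.** The strongest reply has four parts.

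**The event is not hidden.** A reader might infer that it is never counted in the primary safety endpoint. The documents do not support that. SAP 7.1 defines the endpoint as AEs, AESIs and laboratory data, not as TEAEs. The last rows of the table above show where the event still appears, and in a 9-subject trial the listings can be read in full. This stands. What remains is that a listing entry or a pre-treatment row does not give the on-treatment frequency or severity.

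**Worsening of underlying disease is largely outside the gap.** A reader might also infer that pre-existing gastrointestinal, hepatic or catheter problems made worse by the drug are lost. Under Protocol 6.2, a condition present at the initial visit that first worsens after dosing is not barred from being an AE, and its onset would naturally be the worsening. Worsening laboratory values are in the shift tables. This stands, and it limits the gap to AEs that arise between consent and first dose and are ongoing at first dose.

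**The recording convention may already solve it.** If sites open a new record at worsening, the SAP counts it as a TEAE. The SAE report has its own start date (Protocol 6.3.2), and an eCRF completion guideline exists (Protocol 11.2) but is not in the documents. This stands as an uncertainty. Neither document states such a convention, and sites could differ. The rule in SAP 9.3 that partial dates generally default to TEAE helps only where dates are incomplete.

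**The Note to File is unseen.** It supersedes the SAP (SAP Section 2), and SAP 9.8.2 points to it twice. SAP 10 describes it as concerning how AESIs are identified, so there is no sign that it touches the TEAE rule, but this cannot be excluded.

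**Conclusion.** The point holds in a limited form. The TEAE definition has no clause for a pre-dose AE that rises in grade or becomes serious after first dose, and no recording rule in the documents fills the gap. Such an event, kept as one record, is left out of every treatment-emergent and on-treatment table. The effect goes one way: the omission can lower treatment-emergent incidence or severity but cannot raise them.

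The size depends on a count that the documents do not give. It is 11.1 points for each subject newly counted in a row, and zero if no such AE exists or if sites record worsening as a new event. The conclusion assumes that the Note to File leaves the TEAE rule alone and that all 9 enrolled subjects were dosed.

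This should be fixed, but it need not hold up the plan. The analysis is descriptive, and the listings keep the events in view.

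**What to change.** In SAP 9.8.2 and SAP 10, define a TEAE as an AE with onset on or after first dose, or with onset before first dose that increases in CTCAE grade or becomes serious on or after first dose. Apply the same rule to TESAE, treatment-emergent AESI and on-treatment AE.

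Choose one mechanism and state it:

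- reclassify the existing record, so that it counts as a TEAE at its highest post-dose grade and leaves the pre-treatment row; or
- record the worsening as a new AE with its own start date, and leave the earlier record as pre-treatment.

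Doing both would count one event twice in the planned event totals. Reclassifying in programming works only if the database holds the date of the grade change or of becoming serious. The documents do not show that it does, so a site query may be needed.

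Before database lock, check every pre-dose AE that was ongoing at first dose.

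SAP 10 aligned the definition with TA799-007, and SAP 6.1 has the safety data of the trials reviewed together. If that definition must stay for pooling, keep it in the main tables and give the worsening-inclusive counts in a supplementary table.

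The cost is a wording change, limited programming and a few queries in 9 subjects. Because recruitment is closed, any new records mean some retrospective work at the sites. Reported incidence may rise slightly.

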9.8.3 LABORATORY DATA

For laboratory panels (hematology, chemistry, and hemostasis), summary statistics of observed and change from baseline values will be produced by analysis visit up to Week 52 for all continuous variables. For laboratory results reported with a prefix, for example "<" or ">", the value derived from the reported results without a prefix will be analyzed.

Shift tables will display the cross tabulation of Common Terminology Criteria for Adverse Events (CTCAE) grades (based on version 5.0 or higher) from the baseline to worst post-baseline based on the maximum post-baseline grade during the treatment and safety follow-up periods considering both scheduled and unscheduled post-baseline values. The percentages will be calculated based on the number of subjects assessed who have both baseline and post-baseline results.

All laboratory data for hematology & hemostasis, chemistry, urinalysis, endocrinology, and serology will be listed.

There will be separate listings for hematology & hemostasis, and chemistry data with clinically significant results.

9.8.4 VITAL SIGNS AND OTHER SAFETY PARAMETERS

For vital signs (systolic and diastolic blood pressure, heart rate, and temperature) and weight, summary statistics of observed and changes from baseline values will be presented by analysis visit up to Week 52.

All height, weight, and vital signs data will be listed.

Similarly, for each electrocardiogram (ECG) parameter (RR interval, PR interval, QRS interval, QT interval, QTcF interval), summary statistics of observed and changes from baseline values will be presented by analysis visit. In addition, ECG interpretation results will be summarized by frequency (%) for each analysis visit up to Week 52.

All ECG data will be listed.

All physical examination data will be listed.

The relative change from baseline in urine volume (%) will be summarized by analysis visit up to Week 52. The change from baseline and percent change from baseline will be calculated using the average daily urine volume data as per the Balance Period Calculations eCRF.

Subject data listings will be prepared to document data from the 48-hour urine collection diary, 24-hour urine collection diary, balance period calculations, post-PS volume reduction safety evaluation, and PS adjudication.

There will be a separate listing to document PS volume details upon withdraw from trial visits for subjects who have permanently discontinued from trial treatment.

The investigator narratives data will be listed.

Colonoscopy/colonography data will be listed.

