2.2.4 Follow-up Period

Safety follow up assessments will be performed 4 weeks (± 1 week) after the last dose (EOT), except for subjects continuing into the LTE.

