3.5 Withdrawal/Discontinuation of Subjects

Every effort should be made to keep all subjects in the trial.

In case a subject discontinues or withdraws prematurely from the trial treatment for any reason after receiving at least one dose of IMP, the subject should be asked to perform the early termination visit and continue participation in the trial as per the Schedule of Assessments (SoA), i.e., participating in all trial assessments according to the protocol (with the exception of IMP administration) until the planned Week 52 visit.

In cases where this is not possible, the subject should be asked if they would allow the Investigator to continue collecting their weekly PS prescription and/or actual PS administration data once a month (through a phone call to the subject) until what would have been the subject's planned Week 52 visit and to continue to collect the subject's safety data (AEs).

Investigators should observe subjects who discontinue IMP treatment for potential dehydration or fluid overload, and in such case, PS should be managed according to local clinical practice.

If a subject withdraws prior to receiving IMP, the early termination visit is not required.

² Subjects recovered from hepatitis B or C can be enrolled, i.e., they have markers of the infection, but the viral load is undetectable. Subjects with evidence of an acute or chronically active hepatitis B or C infection should be excluded. If a subject is positive for hepatitis A virus immunoglobulin M antibodies, this would indicate an acute infection and the subject is ineligible, but he/she may be eligible for re-screening after recovery. Patients with isolated hepatitis A virus IgG antibodies can be enrolled. A subject positive for hepatitis B antigens, along with an undetectable viral load and a history of vaccination against hepatitis B would be eligible for enrollment.

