7.6.3 Safety Lab Values and Other Continuous Safety Values

All safety continuous endpoints will be presented in summary tables. All data will be used. No missing data will be replaced

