9.2 DEFINITION OF BASELINE, TRIAL VISITS, AND VISIT WINDOWS

The baseline is the last available assessment/observation prior to first trial treatment (i.e. first administration of apraglutide). For assessments done on the same day as the first trial treatment, the time of assessment should be used to recognize whether or not the assessment was done prior to the first trial treatment. Otherwise, when the time of assessment is not available, last available assessments on or prior to the date of first trial treatment will be

considered as baseline since assessments are to be performed prior to dosing on the day of the first IMP administration according to the schedule of assessments in the protocol.

For evaluation of MB parameters, all relevant data measured over the MB period at the scheduled visit will be considered as the analysis timepoint. This applies to baseline, Week 4, and Week 48. The detailed derivation of baseline MB period data can be found in Section 9.7. Except for EOT visit data for efficacy analyses, by-visit efficacy data will be analyzed based on eCRF visits.

For all efficacy analyses, the EOT visit data will be mapped to a visit as defined below and will be only used to replace any missing by-visit efficacy data:

Table 9.2.1: Data Mapping Scheme

Visit	Analysis timepoint	Target day*	
4	Week 2	Day 15	
5	Week 4	Day 29	
6	Week 8	Day 57	
7	Week 12	Day 85	
8	Week 16	Day 113	
9	Week 20	Day 141	
10	Week 24	Day 169	
11	Week 28	Day 197	
12	Week 32	Day 225	
13	Week 36	Day 253	
14	Week 40	Day 281	
15	Week 44	Day 309	
16	Week 48	Day 337	
17	Week 52	Day 365	

*based on the relative days from the first trial treatment where the relative days from the first trial treatment = date of assessment or event – date of first trial treatment + 1, when both dates are known for assessments or events started on or after the day of the first trial treatment. (e.g., Relative Study Day 1 = the first study dosing day)

For safety data analysis, by-visit data will be analyzed based on the assigned analysis visit based on the data mapping scheme above. If more than one assessment falls into allowed time window the closest to the target date will be used. If two values are equidistant from the planned visit/assessment date, the first value will be used.

The citrulline and apraglutide plasma concentration data will be analyzed by scheduled visit based on eCRF visit (including EOT where applicable).

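### Continuous safety data from the 4-week off-drug visit have no row of their own: completers' weight and vital signs are only listed, and early stoppers' values can appear under a treatment-week label

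*SAP*

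**What the plan says.** Protocol 2.2.4 makes the EOT visit the safety follow-up: "Safety follow up assessments will be performed 4 weeks" after the last dose, with a window of one week either side, except for subjects who continue into the long-term extension (LTE). Protocol 5.2.8 has weight, vital signs, ECG, chemistry, hematology and hemostasis measured at that visit. Protocol 7.6.3 sets the reporting rule for continuous safety data: "All safety continuous endpoints will be presented in summary tables. All data will be used".

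The SAP handles these data as follows.

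- **Vital signs and weight (9.8.4):** "summary statistics of observed and changes from baseline values will be presented by analysis visit up to Week 52", plus listings.
- **ECG (9.8.4):** parameters are summarised by analysis visit, and the overall interpretation by analysis visit to Week 52, plus listings.
- **Laboratory values (9.8.3):** "summary statistics of observed and change from baseline values will be produced by analysis visit up to Week 52 for all continuous variables". A CTCAE shift table from baseline uses the "maximum post-baseline grade during the treatment and safety follow-up periods considering both scheduled and unscheduled post-baseline values".
- **Visit assignment (9.2):** "For safety data analysis, by-visit data will be analyzed based on the assigned analysis visit based on the data mapping scheme above". That scheme, Table 9.2.1, runs from Week 2 to Week 52 with no EOT row. The same section keeps EOT as a timepoint for apraglutide concentration and citrulline.

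SAP 10 lists the departures from the protocol's analysis, including small wording corrections. The Week 52 cut-off is not among them.

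**The concern.** Safety and tolerability is the primary objective under protocol version 4, and laboratory results are a primary endpoint. Parenteral support may have been reduced during the year in response to a drug effect that ends when dosing ends. Weight, blood pressure, heart rate and chemistry four weeks off drug bear directly on fluid status at that point. The protocol raises the issue for premature discontinuers in section 3.5: "Investigators should observe subjects who discontinue IMP treatment for potential dehydration or fluid overload".

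As planned, the values collected at the off-drug visit either drop out of the by-visit tables or, for some subjects, enter them without being marked as off drug. In both cases the summary tables cannot show what happened to these measures after the drug was stopped.

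**Working it through.** No sample-size or power figure is involved. The check is day arithmetic on Table 9.2.1, followed by a comparison of the planned outputs.

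**Inputs**
- Target days: Table 9.2.1, 14 rows, Week 2 = Day 15 to Week 52 = Day 365.
- EOT timing: last dose + 28 days, ± 7 days (Protocol 2.2.4).
- Last dose for a completer: Week 51. This is an assumption, based on 52 weekly doses starting at Week 0 and no site injection marked at Visit 17 in the schedule of assessments. A last dose at Week 52 is shown as the alternative.
- Subjects: 2 + 7 = 9 enrolled (SAP 2). LTE entrants have no EOT visit (SAP 4.1).

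**Reproducing the scheme.** Target day = 7 × week + 1. All 14 rows agree, for example 7 × 52 + 1 = 365.

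**Completers.** EOT day = 7 × (last-dose week) + 1 + 28, ± 7.

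| Last dose | Dose day | EOT day (range) | Days after Day 365 |
|---|---|---|---|
| Week 51 | 358 | 386 (379–393) | 21 (14–28) |
| Week 52 | 365 | 393 (386–400) | 28 (21–35) |

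Neither case has a row. If the Week 52 window did reach this far, the rule of taking the assessment closest to target would keep the Week 52 value and leave the EOT value out, provided Week 52 was assessed.

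**Early stoppers.** EOT falls on or before Day 365 when 7w + 29 ≤ 365, that is w ≤ 48. This covers last-dose Weeks 0 to 48, or 49 of the 52 possible last-dose weeks. Some land exactly on a target: last dose Week 8 gives Day 85 (Week 12), Week 20 gives Day 169 (Week 24), and Week 44 gives Day 337 (Week 48). Because safety data are assigned by day, such an EOT value can be reported under that week's label.

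**What an EOT value contributes, for a completer with a Week 52 assessment**

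| Data | By-visit table | Other summary | Listing |
|---|---|---|---|
| Weight, vital signs | No | None | Yes |
| ECG | No row in scheme | None | Yes |
| Laboratory | No | Worst-grade shift, treatment and follow-up pooled | Yes |
| Adverse events | Not applicable | Counted as treatment-emergent, no end date (SAP 10) | Yes |
| Drug concentration, citrulline | Yes, EOT kept | – | Yes |

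**The case against.** The strongest reply is that little is lost. Several points in it stand.

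- A reader might infer that laboratory values at EOT have no summary at all. That is not so: the shift table explicitly includes safety follow-up and unscheduled values. What it cannot show is whether the worst grade arose on or off drug, and it covers only tests that CTCAE grades.
- A reader might infer that harm after stopping goes untabulated. The documents do not support that. SAP 10 removes the end date from the treatment-emergent definition, so a dehydration or fluid-overload event reported after the last dose is counted, and fluid overload is an event of special interest.
- The warning in Protocol 3.5 concerns subjects who discontinue prematurely, and it speaks of potential events. It is not a statement that completers are expected to deteriorate.
- Not every subject outside the LTE loses a summary row. For most early stoppers EOT falls inside the scheme, and the problem is the label. These subjects are also asked to attend scheduled visits to Week 52, so other off-drug values will sit in the same rows.
- Protocol 7.6.3 can be read mainly as a rule against imputation, since it goes on to say that missing data are not replaced. It does not demand a row for every visit.
- With at most 9 subjects, a listing ordered by subject and date lets a reader find each value.

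These points narrow the issue but do not remove it. The SAP states a cut-off and a mapping rule whose effect is to omit or mislabel data already collected at the designated safety visit, while retaining that visit for drug concentration and citrulline.

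**Conclusion.** The point holds for continuous safety data only. For completers not entering the LTE, EOT weight and vital signs are only listed, ECG has no EOT row, and laboratory values enter one pooled worst-grade table. For early stoppers, off-drug EOT values can be reported as treatment-week values.

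The size is modest. Those affected are a subset of the 9 enrolled, and the documents do not say how many entered the LTE, so the number could be anything from 0 to 9 and may well be small. No efficacy result or adverse-event count changes.

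The conclusion rests on three things: the assumed last dose at Week 51 (Week 52 leads to the same conclusion); Table 9.2.1 as it reads in the copy reviewed, where target days are visible but window bounds are not; and the absence of any contrary instruction in the note to file of 6 December 2022. That note overrides the SAP, and its content is not reproduced in Appendix 4.

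**What to change.** First check the note to file and the table shells in case they already deal with this. If they do not:

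1. In SAP 9.2, state that EOT safety data are analysed by eCRF visit, as for drug concentration and citrulline, and are not assigned to a treatment week.
2. In SAP 9.8.3 and 9.8.4, add a separate EOT (4 weeks off drug) row to the laboratory, vital-sign, weight and ECG tables. Show the number assessed, the change from baseline and the change from the last on-treatment value.
3. In SAP 9.8.3, show the worst CTCAE grade separately for on-treatment and follow-up.

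If the sponsor prefers to keep the Week 52 cut-off, SAP 10 should declare it against Protocol 7.6.3.

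The cost is a few lines of SAP text and a few extra rows, some with very small n. No new data are needed, and nothing in the handling of subjects changes.
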